3.1 Inclusion Criteria

The subject must fulfil all the following criteria to be included in the study:

- 1. Volunteer to participate in clinical study; thoroughly informed, signed and dated the informed consent form; willing to follow and have the ability to complete all trial procedures.
- 2. Suspicious or confirmed patients with bladder cancer.
- 3. Age 18 or older.

3.2 Exclusion Criteria

Patients presenting with any of the following will not be included in the study:

- 1. Gross haematuria. (Note: Gross haematuria is defined as a heavy bladder bleed resulting in marked amounts of blood in the urine, which may visually limit cystoscopy. Where the haematuria is light, the patient should not be excluded, if in the investigator's opinion, rinsing and/or electro-cautery during cystoscopy will alleviate the possible interference with cystoscopy).
- 2. Patients who have received BCG immunotherapy or intravesical chemotherapy within the past 6 weeks prior to the procedure.
- 3. Porphyria.
- 4. Known allergy to hexaminolevulinate hydrochloride or a similar compound.
- 5. Pregnancy or breast feeding or patients of child-bearing potential, including men with partners of child-bearing potential, who are unwilling to take barrier contraceptives from 2 weeks before medication to 28 days after the medication. (Note: Child-bearing potential is defined as females who are ovulating, pre-menopausal or not surgically sterilized. All women of child-bearing potential must document a negative pregnancy test before study inclusion and use adequate contraception during the study).
- 6. Participation in other clinical studies with investigational drugs/investigational device either concurrently or within the last 30 days prior to the first study cystoscopy.
- 7. Patient is the investigator or any sub investigator, research assistant, pharmacist, study coordinator, other staff or relative thereof directly involved in the conduct of the protocol.
- 8. Patients that the investigator assessed unsuitable to the study.
- 9. Subjects with contraindications to white light cystoscopy.

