Patients	1. Gross haematuria. (Note: Gross haematuria is defined as a heavy bladder bleed resulting in marked amounts of blood in the urine, which may visually limit cystoscopy. Where the haematuria is light, the patient should not be excluded, if in the investigator's opinion, rinsing and/or electro-cautery during cystoscopy will alleviate the possible interference with cystoscopy).
	2. Patients who received BCG immunotherapy or intravesical chemotherapy within 6 weeks prior to the procedure.
	3. Porphyria.
	4. Known allergy to hexaminolevulinate hydrochloride or a similar compound.
	5. Pregnancy or breast feeding or patients of child-bearing potential, including men with partners of child-bearing potential, who are unwilling

tudy Number: YF	C1-HEX-B1 V 2.2, Feb 6 th 202
udy Number: YF	after the medication. (Note: Child-bearing potential is defined as women who are ovulating, pre-menopausal or not surgically sterilized. All women of child-bearing potential must document a negative pregnancy test before study inclusion and use adequate contraception during the study). 6. Participation in other clinical studies with investigational drugs/investigational device either concurrently or within the last 30 days prior to the first study cystoscopy. 7. Patient who is the investigator or any sub investigator, research assistant, pharmacist, study coordinator, other staff or relative thereof directly involved in the conduct of the protocol.
	8. Patients that the investigator believed were unlikely to comply with the protocol.
	9. Subjects with contraindications to white light cystoscopy.
Drug / Device	Drug name: Hexvix (hexaminolevulinate hydrochloride, for intravesical solution, for bladder instillation only) as the photosensitizer to use with blue light cystoscopy Active ingredient: Hexaminolevulinate hydrochloride Device: Cystoscopic equipment with necessary filters to allow both standard white light cystoscopy and blue light (wavelength 380–450 nm) fluorescence cystoscopy
Comparative Drug	Not applicable
	Primary Efficacy Endpoint:
	• The proportion of patients with histology-confirmed tumors (Ta, T1, or CIS) who have at least one such tumor found by Hexvix but not by white light cystoscopy.
E.C. acces	Secondary Efficacy Endpoint:
Efficacy Endpoint	• The proportion of patients with one or more CIS lesions detected only by Hexvix blue light cystoscopy not by white light cystoscopy.

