4.3.1 Diagnosis and Pre-treatment Evaluation (visit1)

Pre-treatment evaluation at Visit 1 will only be performed after the patient has agreed to participate,

Study Number: YHCT-HEX-B1

has signed and dated the informed consent form. No treatment will be initiated before the informed consent has been given.

Pre-treatment evaluation will be performed according to the inclusion and exclusion criteria, including:

- 1. Patient informed consent.
- 2. Record demography information (gender, age, ethnicity, height, weight, body mass index, and history of allergies, drug abuse, smoking, alcohol abuse, and blood donation), medical history, and surgery history.
- 3. Record medication history.
- 4. Vital signs include: body temperature, sitting blood pressure, heart rate, and breathing rate. Vital signs should be measured when the investigator judges that the subject's condition is stable.
- 5. Physical examination: general conditions, head and neck, lymph nodes, skin, chest, abdomen, musculoskeletal system (including limbs and spine) and nervous system.
- 6. Pregnancy test (only for women of childbearing age): The pregnancy test for women of childbearing age during the screening period must be negative. If the subject has undergone a pregnancy test within 7 days before the administration, visit 2 can no longer perform the test. During the study period, urine pregnancy test can be performed as needed. If the urine pregnancy result is positive, a serum pregnancy test is required to confirm. If it is confirmed positive, the subject needs to withdraw from the test, and the investigator will continue to follow up the subject until the end of the pregnancy.

Note: Women of childbearing age must take effective contraceptive measures during the study period.

- 7. Review the inclusion and exclusion criteria.
- 8. Record complications, adverse events and concomitant medications/procedures.

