8.5 Sensitization Risks and Management Measures

Hexvix[®] has the potential to cause rapid-onset severe allergic reactions / hypersensitivity reactions, for which the Sponsor has developed a risk management plan and is managing this as a "significant identified risk".

The routine risk preventive measures that the Sponsor takes concerning this risk are as follows:

- 1. In this clinical trial, subjects with allergy to hexaminolevulinate hydrochloride or a similar compound will be excluded;
- 2. The information on the safety profile of Hexvix concerning allergy occurring in preclinical studies, clinical studies and postmarketing exposure is fully described and prompted in the investigator brochure.
- 3. Information on risks is provided in the clinical use instructions: 【Contraindications】 Hypersensitivity to the active substance or to any of the excipients. Porphyria. 【Special warnings and precautions for use】 The possibility of hypersensitivity including serious anaphylactic/anaphylactoid reactions should always be considered. Advanced life support facilities should be readily available. 【Undesirable effects】 Adverse reactions from clinical trials and spontaneous reporting: immune system disorders anaphylactoid shock.

Study Number: YHCT-HEX-B1

9. Data Management

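### The allergy exclusion (criterion 4) is narrower than the contraindication quoted in Section 8.5, so a patient with known excipient hypersensitivity can meet the written criteria and be instilled

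*Combined protocol and SAP*

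**What the plan says.** Criterion 4 reads the same in the synopsis and in Section 3.2: "Known allergy to hexaminolevulinate hydrochloride or a similar compound".

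Section 8.5 states that the product "has the potential to cause rapid-onset severe allergic reactions / hypersensitivity reactions", and that the sponsor handles this under a risk management plan as a significant identified risk. It then lists three routine preventive measures:

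- The first is exclusion from the trial: "In this clinical trial, subjects with allergy to hexaminolevulinate hydrochloride or a similar compound will be excluded".
- The second points to the safety information in the investigator brochure.
- The third reproduces the clinical use instructions, whose contraindications are "Hypersensitivity to the active substance or to any of the excipients" and, separately, porphyria.

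Criterion 8 has two versions. Section 3.2 has "Patients that the investigator assessed unsuitable to the study". The synopsis has "Patients that the investigator believed were unlikely to comply with the protocol".

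At Visit 1 (Section 4.3.1) the demographic record includes "history of allergies, drug abuse, smoking, alcohol abuse, and blood donation".

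**The concern.** Hypersensitivity is the one risk to which the protocol gives its own management section, and exclusion at screening is the first measure against it. That exclusion does not reach as far as the contraindication printed two items below it. A site that works strictly from the numbered criteria has no instruction to turn away a patient whose known hypersensitivity is to an excipient and who has never had the active substance.

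What is at stake is subject safety and the coherence of the eligibility text. Such a patient would also not count as an entry violation, because no criterion would have been broken. No estimate, test or sample size depends on the point.

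**Working it through.** No arithmetic applies. The check takes the contraindication quoted in Section 8.5 apart and asks, for each element, which mandatory criterion enforces it.

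| Element of the quoted contraindication | Mandatory exclusion that covers it |
|---|---|
| Hypersensitivity to the active substance | Criterion 4 |
| Porphyria | Criterion 3 |
| Hypersensitivity to an excipient | None of criteria 1 to 9, in the synopsis or in Section 3.2 |

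**Could other wording close the third row?**

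1. The reference to similar compounds in criterion 4 is undefined. Its natural meaning is substances chemically like hexaminolevulinate, not the other ingredients of the kit.
2. Criterion 9 excludes patients with a contraindication to white light cystoscopy. There is no parallel criterion for a contraindication to the drug.
3. The device restrictions in Section 5.2 cover earlier immunological reactions to photosensitizers. They do not mention excipients.

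**Could a discretionary provision stop such a patient?**

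1. Criterion 8 in Section 3.2 could, if the investigator judges the patient unsuitable. The synopsis version could not, because it concerns compliance only.
2. Section 3.4 lets the investigator withdraw a subject before dispensing if continuing is thought harmful. This too is a judgement.
3. The allergy history at Visit 1 could bring the problem to light, but no criterion on excipients acts on it.
4. The use instructions quoted in Section 8.5 carry the wider contraindication, but the protocol does not turn it into an eligibility rule. Sections 5.1.1 and 5.1.2 refer to the drug instructions for administration and storage, not for eligibility.

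**Who is exposed?** Section 6.1 has all eligible subjects instilled. Section 4.2 places instillation before randomization, so subjects who do not go on to blue light also receive the drug. Under Section 5.1.1 the kit is an 85 mg powder reconstituted with a 50 mL prefilled solvent, so each subject receives more than the active substance.

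**How many could be affected?** The planned denominator can be read off: about 380 subjects, plus at least 4 training subjects at each of about 5 to 10 centers, or 380 + 20 = 400 to 380 + 40 = 420. The 380 includes a 5% drop-out allowance, so actual instillations may be fewer. The numerator cannot be obtained: the documents do not name the excipients or the solvent's contents, and give no frequency of known allergy to them.

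**The case against.** The best defence is that the three measures in Section 8.5 apply together. The third puts the wider contraindication in front of every site, the allergy history is taken from every subject, and Section 3.2 gives the investigator a written ground to exclude. Nothing in the protocol says that a patient with an excipient allergy should be instilled. On this view the texts are poorly harmonised but do not conflict.

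Much of this stands. A reader might infer that a contraindicated patient will pass screening and be given the drug. The documents do not support that: an attentive investigator has both the information and the authority to prevent it. A reader might also try to put a count on the patients at risk, but any frequency would be a guess while the excipients are unnamed.

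Nor is it a fault of the per-protocol sets (Section 10.3.3) that they would not pick up such a case. They are efficacy sets; every instilled subject is in the safety set (Section 10.3.1), and adverse events are recorded for all.

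What the defence does not remove is that every safeguard it names depends on judgement. Other contraindications (porphyria, allergy to the active substance) are mandatory exclusions, while this one is left to discretion without explanation. The main discretionary safeguard also reads differently in the synopsis.

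**Conclusion.** The mismatch is confirmed by reading the synopsis, Section 3.2 and Section 8.5 together. The mandatory allergy exclusion and the first preventive measure are narrower than the contraindication quoted in the third, and no other mandatory criterion makes up the difference. A patient with known excipient hypersensitivity can meet the written criteria and be instilled; whether that happens depends on the investigator.

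The conclusion rests on one reading, that a similar compound means one like the active substance. If the sponsor intended the phrase to include excipients, the gap lies in the drafting only, and the text should say so.

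The number affected cannot be estimated and may be very small. The point is worth correcting because of the weight the protocol gives this risk, not because of any expected count.

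**What to change.** The sponsor should reconcile criterion 4 (synopsis and Section 3.2) and the first measure of Section 8.5 with the contraindication quoted in the third measure, so that the mandatory eligibility text and the quoted contraindication agree. The two versions of criterion 8 should be reconciled at the same time. The right scope of the exclusion is a clinical matter for the sponsor to decide; the request is only that the passages agree.

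The cost is a minor wording change in three places for the allergy text, and in the synopsis or Section 3.2 for criterion 8. Allergy history is already collected at Visit 1, so no new procedure is needed. The effect on enrolment should be negligible, though the documents give no figure to confirm this. The sample size and the primary analysis are unchanged.

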3.3 Elimination criteria

Data will be submitted to the principal investigator, sponsor and statistical institution during data review meeting to determine if there is any individual case that needs to be eliminated before statistical analysis of the data is performed.

3.4 Withdrawal criteria

Version 2.2 Date: Feb 6th, 2023

Study Number: YHCT-HEX-B1

1) Investigator's decision to withdraw

Withdrawal from the study refers to the fact that the selected subjects are unsuitable to continue the study during the course of the study, and the investigator decides to withdraw the case from the study. For subjects withdrawn from the study, the investigator should fill in the reason for withdrawal in the electronic case report form (eCRF), complete the evaluation items that can be completed, and fill in the end-of-treatment follow-up record form including the last time of contact. In the following, the criteria for the investigator's decision to withdraw are listed. Beware that this is only applicable before dispensing of the Investigational Drug and Device.

- The investigator believes that continuing treatment will be detrimental to the subject. [such as in the clinical trial, the subject has some comorbidities (documented as medical history), complications or worsening of the condition, and it is not suitable to continue the trial. (Note: this is only applicable to the time frame between Visit 1 and Visit 2. It stays unchanged that comorbidities should be evaluated accordingly before inclusion. Complications or worsening of the condition of the patient (AE) after dispensing of the Investigational Drug and after the procedure should not lead to a withdrawal of the patient, but should stay in the study for the Follow Up of AEs or complications for safety reasons.)]
- Major protocol deviations.
- The subject did not follow the doctor's advice and used other treatments without authorization, which affected the evaluation.
- The subject's poor compliance affects the efficacy and safety assessments.
- Other. (Note: The specific reason should be recorded in the "Specific Description" section of the electronic case report form (eCRF), for example: non-compliance.)

2) Subject's decision to withdraw

Subjects, unwilling to continue to participate in clinical research, have the right to withdraw from the study at any time of the study according to the provisions of the informed consent form, or subjects have not explicitly asked to withdraw from the study, but no longer undergo test and lost to follow-up, also belonging to "withdraw" (or "drop out"). The reasons for their withdrawal should be understood as much as possible and recorded. Such as consciously feel intolerable to some adverse reactions; unable to continue to receive clinical study due to other reasons; or lost to follow-up without explaining the reason, etc.

3) Handling of withdrawal cases

Subjects, unwilling to continue to participate in clinical research, have the right to withdraw from the study at any time of the study according to the provisions of the informed consent form, or subjects have not explicitly asked to withdraw from the study, but no longer undergo test and lost to follow-up, also belonging to "withdraw" (or "drop out"). The reasons for their withdrawal should be understood as much as possible and recorded. Such as consciously feel intolerable to some adverse reactions; unable to continue to receive clinical study due to other reasons; or lost to follow-up without explaining the reason, etc. Regardless of the reason, for withdrawal cases, the case report form should be retained, and the last examination result transferred as the final result, and full data analysis of the efficacy and

Study Number: YHCT-HEX-B1

adverse reactions should be conducted.

All study-related toxicity and serious adverse events (SAE) that existed at the time the study was discontinued must be followed up to their resolved, unless, according to the investigator's opinion, the condition cannot be remitted because of the subject's disease itself.

After the subject terminates the study treatment, the investigator must follow up all existing or new AEs during the study period. And report all new AEs and SAEs that occurred within this period of time (if an SAE, it must be reported to the sponsor in time, and tracked until the above-mentioned adverse events are resolved.) After subject terminates the study, the investigator must immediately notify the sponsor. Any SAE needs to contact the sponsor in time with the corresponding SAE reporting process.

There will be no replacement of withdrawn patients.

3.5 Early Termination of Study/ Closure of Study Center

The sponsor has the right to terminate this study at any time, and the sponsor and the investigator have the right to close the study center at any time. Of course, this situation can only be implemented after mutual negotiation. When terminating the study, the independent ethics committee (IEC) and the institutional review board (IRB) must be reported. The ethics committee has the right to suspend or terminate clinical trials that are not implemented in accordance with relevant requirements or that the subjects have suffered unexpectedly severe damage. When the study is terminated early or the study center is closed early, all study materials (except for the documents that must be kept in the center) must be returned to the sponsor. The investigator must keep other documents until notified by the sponsor to destroy it. The reasons leading to the early termination of the trial or the closure of the study center can be, but not limited to, the following reasons:

- New information leads to unfavorable risk-benefit assessments of the investigational drug, for example, due to:
 - The investigational drug lacks efficacy, whether in this study or other studies;
 - The occurrence of significant previously unknown adverse reactions or unexpectedly higher severity/incidence of known adverse reactions; or
 - Other adverse safety findings, including clinical examination and non-clinical manifestations;
- The sponsor believes that it is unreasonable to continue the above study due to Health care, ethical, or commercial reasons;
- It is unlikely that the study will be completed within an acceptable time frame due to the difficulties in enrolling subjects;
 - Suspended or terminated at the request of the health authority.

3.6 Definition of The End of the Study

The end of the study is defined as the last subject who completes his/her last visit, unless the end of the study is for a reason in Section 3.5.

Study Number: YHCT-HEX-B1

4. Study Design

4.1 Study Type and Design Principle

A Prospective, within patient controlled multicenter study.

This study includes 3 regular visits: screening visit(-2w), cystoscopic examination (day 0), safety follow-up(1w). Study design as below:

[figure not shown]

Fig2. Study design

At the start of the study, a minimum of four subjects included at each center will be training subjects. These subjects will receive the Hexvix administration and undergo white and blue light cystoscopy with tumor resection as below. They will receive the same safety follow up as all the other included patients, after completing the safety follow-up for 1 week, the patients will be treated according to hospital's clinical routine by the Investigator. These patients are not part of the efficacy analyses.

To reduce possible bias in assessment of the objectives, a small number of subjects will be randomized to not continue with Hexvix blue light cystoscopy following white light cystoscopy.

Consented, eligible subjects (Visit 1) will be instilled with 50 mL Hexvix 8 mM solution for one hour. After bladder evacuation, the following procedure will be utilized to accomplish the cystoscopic examination of each subject:

1. Turn on the white light. Inspection of the bladder and mapping of all papillary lesions and flat and suspicious lesions seen under white light, record lesion number, size and location.

2. Randomization:

- a) If the patient is not randomized to undergo blue light mapping, proceed to step 3.
- b) If the patient is randomized to continue with blue light mapping, or subjects for investigator training procedure, then they will undergo blue light cystoscopy. Turn to the blue light. Inspection of the bladder and mapping of all papillary lesions and flat and suspicious lesions seen under blue light, record lesion number, size and location.
- 3. All papillary lesions detected will be resected using TURBT and all flat and suspicious lesions detected will be biopsied. The lesions resected and biopsied should be marked and pathologically examined separately. For patients randomized to undergo blue light cystoscopy and for training patients, the completeness of the resection should always be checked under blue light before finalizing the TURBT procedure until it is ensured that all lesions and

Study Number: YHCT-HEX-B1

suspicious areas are completely resected. Both biopsied and resected tissue will be examined by the local pathologist, then evaluated by independent and blinded central pathologists. Central pathology results will be used as reference standard in the study efficacy endpoints.

All subjects (including the training patients) will receive a safety follow-up at day 7 (visit 3) after day 0 cystoscopy (visit 2), after completing the safety follow-up for 1 week, the patients will be treated according to hospital routines by investigator.

Training subjects are not included in the randomization procedure and efficacy analysis, but included in the safety analysis.

